**Background:** Undiagnosed and untreated depression is a significant cause of morbidity and mortality in low-middle-income countries (LMIC) such as India. The rates of diagnosis and treatment of depression among women in rural India are disproportionately low despite a primary care based task-sharing model of mental-health treatment. Stepped care approaches support appropriate treatment of symptoms while reducing the burden on healthcare systems and mobile technology can reduce the mental health treatment gap given its reach and easy access. However, as our preliminary study at a task-sharing care model in rural south India (Maanasi clinic, situated 60 miles from Bangalore city) revealed: illiteracy and the practice of sharing mobile phones as a family resource present hurdles to the adoption of mobile mental health (mHealth) based interventions. *To date, the feasibility of an mHealth application to screen depression, track symptom severity and support the delivery of stepped care treatment has not been tested in LMIC.*

**Specific Aim 1:** In phase I of this exploratory study, we will adopt a user centered participatory approach to design and develop a multiple-user, voice-response, mobile application (“MITHRA”), to be used in community-based organizations for screening, tracking and supporting stepped care treatment for depression, including select modules of the Healthy Activity Program, a brief psychological intervention based on behavioral activation. The application will include audio, video and enhanced touchscreen capabilities, to overcome the barrier of illiteracy and lack of access.

**Specific Aim 2:** In phase II, using a randomized-control design, we will examine feasibility and utility of “MITHRA” deployed at community-based organizations (n=3) vs enhanced usual care (n=3) in different villages supported by the Maanasi program (enrolling approximately 60 women).

**Specific aim 3:** Throughout the duration of the funding period we will arrange for mentored participation of Psychiatry and Community Medicine residents from India in the research project. Community Health workers will benefit from regular videoconference didactic and case presentation (ECHO) sessions such as symptoms of and treatment for common mental disorders.

The grant will accomplish the goals of developing a unique mobile application that is scalable, examining its feasibility and building research capacity at the research site in India.

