## 4 RECRUITING and SCREENING PARTICIPANTS

**4.1 Recruiting and Screening.** Describe how subjects will be identified, recruited, and screened. Include information about: how, when, where, and in what setting. Identify who (by position or role, not name) will approach and recruit subjects, and who will screen them for eligibility.

End user focus group: Women for the end user focus group will be recruited from via i) advertisements ii) flyers iii) word of mouth and iv) community health workers (CHWs). We will oversample for women with depressive symptoms such that we have an equal number of women with Patient Health Questionnaire -9 (PHQ-9) score above 5 and PHQ-9 score below 5. [For prescreening](#), to identify women with a PHQ-9 above 5, [community health workers located in the Community Based Organization \(CBO\) will use the PHQ-9 questionnaire](#), introduced with talking points which have been [uploaded](#).

Provider focus group: Primary care and mental health providers will be recruited from Anekal Primary Health Center and CHWs will be recruited from the Community Based Organizations (CBOs) and by contacting them through the parent Mahila Mandal Organization.

All advertisements and flyers will be reviewed and approved before use by the Human Subjects division at University of Washington.

For the RCT, participants will be recruited from community-based organizations (CBOs) via i) advertisements ii) flyers iii) word of mouth and iv) community health workers (CHWs). Our recruitment strategies will enable us to recruit women with varying degrees of depression and to be representative of women in the villages covered by the CBO.

All advertisements and flyers will be reviewed and approved before use by the Human Subjects division at University of Washington.

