CHWs will administer the PHQ9, if more than one woman PHQ9 positive then CHW will proceed with informed consent for all members of SHG. The CHW will use the attached talking points to obtain verbal consent from participants.

a. Documentation of consent. Will a written or verifiable electronic signature from the subject on a consent form be used to document consent for the recruiting and screening procedures?

No

→ If no, describe the information that will be provided during the consent process and for which procedures.

Yes

→ If yes, upload the consent form to [Zipline](#).

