Randomized trial: We will randomize CBOs to use MITHRA (n=3) or enhanced usual care (EUC) (n=3) for 12 weeks. Randomization will be clustered to account for distance from the PHC. The MITHRA CBOs will each have 2 -3 tablets for use by all attendees. A CHW will be present at meetings and encourage women to use the MITHRA app. During their time at the meeting, women will complete the PHQ-9 screening and modules based on their individual depression score. Privacy will be ensured. They will also have the option to take turns checking out the tablet for viewing at home (if this is reported by the design group to be a desirable feature). In the EUC CBOs, CHWs will offer monthly group education (45 min) regarding the symptoms of depression, informed by training webinars led by study Investigators. We have the support of the CBO and PHC leadership for this project (see attached letters of support). In both MITHRA and EUC CBOs CHWs will conduct community outreach to encourage women to attend meetings, as depression can lead to amotivation and women with depression may be less likely to attend CBO meetings. All CHWs will receive training in depression, screening and common treatments, resources and referrals.

**Outcome Measures:** CHWs will maintain rosters of CBO attendees at MITHRA CBOs and EUC CBOs. In monthly review sessions with the study investigators, the CHWs will review questionnaire completion and scores, and directly contact the woman (by phone or home visit or at a CBO meeting) if there is a need to step up care beyond that advised by the app. Women typically attend CBO meetings 2 -3 times a month and use at every attendance will be encouraged.

**MITHRA** is an app which will be available on 2 -3 tablets placed in Community Based Organizations (CBOs). Women can log in to MITHRA using a unique password protected secure single user sign on (fingerprint sign in to account for varying levels of literacy) to complete the physical health questionnaire and the PHQ -9 (validated Kannada version of the PHQ-9) in an assigned private place in the CBO. On completion of the PHQ-9, each woman will receive a prompt based on her total score (see Fig). Women who score < 5 will watch general information on depression; women who score 5 – 10 will watch modules 1 and 2 (case descriptions, What is Depression? and Introduction to PHQ-9) Women who score 10 – 15 will watch modules 1, 2, and 3 (Connection between activity and mood).

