**Statistical Methods:**

Assumptions of normality was assessed using Q-Q plot. Descriptive statistics, mean and standard deviation for normally distributed variables were used to describe the outcome parameters PHQ, QIDS. WHODAS and BADS. Chi-square test or Fisher's exact tests as appropriate, was used to test the association between baseline characteristics between study groups. At each time of assessment, outcome parameters were compared between study groups using independent t test or Mann Whitney U test as appropriate. Change in the outcome at 3 and 6 months from baseline was compared between the study groups using Wilcoxon signed rank test. McNemar Chi-square test was used to compare the change in the proportion of depression categories from baseline within each study group. In addition, RMANOVA was performed to compare the change in the outcome scores over time between study groups. A p-value of  $< 0.05$  was considered statistically significant. All analyses were performed using SPSS version 26.0.

---

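### A Q-Q plot appears to choose t test or Mann-Whitney separately for each outcome and visit, and no between-arm difference with a confidence interval is specified

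*Combined protocol and SAP*

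**What the plan says.** The Statistical Methods section begins with the distributional check: "Assumptions of normality was assessed using Q-Q plot". For each assessment time it then states that "outcome parameters were compared between study groups using independent t test or Mann Whitney U test as appropriate". Nothing else says when each test is appropriate. The natural reading is that the plot decides, outcome by outcome and visit by visit. This is implied rather than written as a rule: there is no cut-off, no named reader, and no statement of whether raw scores or residuals are plotted.

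The criterion for a finding is "A p-value of $< 0.05$ was considered statistically significant". Means and SDs are planned as descriptive summaries of normally distributed variables. No between-arm difference or confidence interval is requested for any outcome, and no analysis is named as primary. The same section adds a repeated-measures ANOVA of scores over time between arms, which is not tied to the plot.

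Three design features bear on this:

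- **Size and allocation.** Aim 2 (section 1.5) gives "enrolling approximately 60 women". Section 5.1 says "We will randomize CBOs to use MITHRA (n=3) or enhanced usual care (EUC) (n=3) for 12 weeks".
- **Entry.** Section 4.7 says "if more than one woman PHQ9 positive then CHW will proceed with informed consent for all members of SHG". Section 4.1 expects recruitment to let the team "recruit women with varying degrees of depression and to be representative of women in the villages covered by the CBO". The PHQ-9 condition applies to the CBO, not to the individual woman.
- **Content by score.** Section 5.1 says "Women who score < 5 will watch general information on depression". Numbered modules begin at a score of 5 and extend as the score rises.

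**The concern.** If the data choose the test, the analysis of one outcome can be a comparison of means at 3 months and a comparison of ranks at 6 months. Those are different hypotheses, and their results cannot be read as one course over time. If the choice falls on Mann-Whitney, the per-visit result carries no effect in score points, which is what a pilot most needs to pass on to the next trial.

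Sensitivity is a second question. Unselected entry suggests many scores near the floor, and the content is graded by score. If benefit sits only in symptomatic women, lowering their scores while most stay above the low scorers changes few ranks, so a rank test sees less of it than a comparison of means.

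**Working it through.** **1. What the documents supply.** They state no power, effect size, SD or share of symptomatic women, so there is no figure to reproduce. From them come about 60 women (30 per arm if equal), 3 against 3 CBOs, the 0.05 level (two-sided assumed), and visits at baseline, 3 and 6 months (section 5.4, QIDS). All else below is assumed. Clustering by CBO is ignored throughout, so the powers serve only to compare tests.

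**2. Is skew likely?** Section 1.8a puts a CBO at about 15 to 20 members. More than one positive woman guarantees only 2/20 = 10% to 2/15 = 13% positive. In an assumed mixture (low scorers 0–4; symptomatic women mean 11, SD 4), control-arm skewness is about 2.2, 1.7, 1.2, 0.8 and 0.5 with 10%, 20%, 30%, 40% and 50% symptomatic. A Shapiro test, as a stand-in for the plot, rejects normality in 96–100% of trials up to 40% symptomatic and in 79–100% at 50%. At 70% skewness is about 0 and a switch is less certain.

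**3. One scenario by hand.** Assume 30% symptomatic (mean 13, SD 3.5), the rest Poisson with mean 3, and a 6-point fall in symptomatic women only.

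- Mean difference: 0.30 × 6 = 1.8.
- Control variance: 0.3 × 12.25 + 0.7 × 3 + 0.21 × 10² = 26.8. Treated variance: 0.3 × 12.25 + 0.7 × 3 + 0.21 × 4² = 9.1. Pooled SD: √((26.8 + 9.1)/2) = 4.24.
- t test: 1.8/4.24 × √(30/2) = 1.645. Power ≈ Φ(1.645 − 2.002) = 36%.
- Mann-Whitney: P(control > treated) + ½P(tie) ≈ 0.09 × 0.887 + 0.21 × 0.995 + 0.21 × 0.153 + 0.49 × 0.5 = 0.566 (normal approximations). Null SE: √(61/(12 × 30 × 30)) = 0.075. Power ≈ Φ(0.066/0.075 − 1.96) = 14%.

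Simulation of the same model gives 33% and 14%.

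**4. How far this depends on the pattern of effect.** Same model, 30 per arm, simulated:

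| Effect | Share symptomatic | t test | Mann-Whitney |
|---|---|---|---|
| 6 points, symptomatic only | 12% | 10% | 6% |
| 6 points, symptomatic only | 30% | 33% | 14% |
| 6 points, symptomatic only | 40% | 51% | 26% |
| 6 points, symptomatic only | 70% | 93% | 86% |
| 4 points, symptomatic only | 30% | 16% | 8% |
| 4 points symptomatic, 1 point low scorers | 30% | 34% | 35% |
| 2 points in every woman | 30% | 29% | 59% |

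A smooth gamma model with effect only at baseline scores of 5 or more gives a smaller gap in the same direction. Mann-Whitney against t is 10% and 15% (29% symptomatic), 14% and 22% (37%), and 22% and 34% (45%).

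**5. What the planned repeated-measures ANOVA recovers.** With two time points its group-by-time test equals a t test on change. With an assumed baseline correlation of 0.5 in symptomatic women, its power is about 50% in the 30%, 6-point scenario.

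**6. Baseline adjustment.** In the step 2 mixture (30% symptomatic, scores halved in symptomatic women only), Mann-Whitney has 9% power, the t test 32%, the change-score t test 52% and ANCOVA on baseline 70%. Under the uniform 2-point shift of step 4, baseline adjustment gives about 75% against 59% for Mann-Whitney.

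**7. The missing estimate.** A Hodges-Lehmann shift added to Mann-Whitney would not stand in for the mean difference. In the 30%, 6-point scenario it averages 0.71 points while the mean difference is 1.77.

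**The case against.** The case against a power argument is strong, and most of it stands.

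- **The plan does not rest on Mann-Whitney alone.** The repeated-measures ANOVA compares means whatever the plot shows, and in the headline scenario it is more powerful than the per-visit t test. It offsets the loss only partly: it is an added analysis, not named primary, with no difference or interval requested.
- **A score of 5 is not a clean treatment boundary.** Low scorers in MITHRA CBOs still receive general information, are encouraged by a health worker to use the app, and can move into the modules on re-screening. A 1-point gain among them removes the gap.
- **The inputs are assumed.** At the 10–13% positive that the entry rule guarantees, neither per-visit test has useful power.
- **The plot is not a written switching rule.** A numeric normality test only approximates a plot read by eye, and skew is not shown for BADS or WHODAS.
- **Aim 2 concerns feasibility and utility.** Individual-level powers with 3 against 3 CBOs describe no valid analysis.

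A reader might infer that Mann-Whitney is the wrong or weaker test for this trial. The documents do not support that: they state no pattern of effect, and the ranking of the tests reverses across plausible patterns. A reader might also infer that the test would be picked by its p-value. Nothing in the text suggests it; the gap is only that the choice is left to the data.

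None of this supplies a fixed comparison or an effect estimate.

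**Conclusion.** The point holds for the per-visit between-arm comparison. As written, the test can differ between visits of one outcome, and a Mann-Whitney result would give this pilot no effect in score points. That conclusion needs no power calculation. It rests on reading the Q-Q plot as the criterion for the choice, which is the only one offered.

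A switch to Mann-Whitney is likely for PHQ and QIDS if up to about half the women are symptomatic. The loss of sensitivity is conditional: 14% against 33% power in the 30%, 6-point scenario, about nil if low scorers gain 1 point, and in Mann-Whitney's favour under a uniform shift. It is a secondary reason to change the plan, not the main one.

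**What to change.** Change the Statistical Methods wording as follows:

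- Remove the plot-based choice of test.
- For each score at 3 and at 6 months, report the between-arm difference in mean score with a 95% CI, adjusted for the baseline value of that score. Section 5.4 already collects QIDS at baseline. The planned change-from-baseline analyses presume a baseline for the other scores; confirm this for BADS and WHODAS, whose timing section 5.4 does not give.
- Compute the difference and interval by a method that respects randomisation of CBOs. With six CBOs, a comparison of CBO-level summaries has 6 − 2 = 4 degrees of freedom, so the interval will be wide and should be reported as such.
- Use Q-Q plots on residuals, as a check and not as a selector.
- Keep Mann-Whitney as a labelled sensitivity analysis.

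The cost is SAP text; there are no new data or visits. An unadjusted mean comparison would lose power to the rank test under a uniform shift (29% against 59% in the assumed model). Baseline adjustment recovers this in simulation (about 75%), given an assumed baseline correlation of 0.5 in symptomatic women and ignoring clustering. Fixing the test does not rescue power if few women are symptomatic.

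### The Wilcoxon signed-rank test named for comparing change between arms is a paired test, the arms are not paired, and the text does not show which test was run

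*Combined protocol and SAP*

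**What the plan says.** The Statistical Methods paragraph lists four analyses of the outcome scores, in this order:

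- Level at each visit, between arms: "At each time of assessment, outcome parameters were compared between study groups using independent t test or Mann Whitney U test as appropriate".
- Change from baseline: "Change in the outcome at 3 and 6 months from baseline was compared between the study groups using Wilcoxon signed rank test".
- Depression categories, within arms: "McNemar Chi-square test was used to compare the change in the proportion of depression categories from baseline within each study group".
- Course over time, between arms: "In addition, RMANOVA was performed to compare the change in the outcome scores over time between study groups".

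Section 5.1 (Randomized trial) gives the allocation: "We will randomize CBOs to use MITHRA (n=3) or enhanced usual care (EUC) (n=3) for 12 weeks". It adds: "Randomization will be clustered to account for distance from the PHC". Specific Aim 2 in section 1.5 places the two sets of CBOs in different villages and expects about 60 women in all. No section defines matched pairs of women across arms, and no other section names a test for change scores.

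**The concern.** The signed-rank test ranks differences within pairs, or one sample's deviations from zero. The women using MITHRA and those in enhanced usual care are separate groups with no partner in the other arm, so the sentence joins a paired test to an unpaired comparison.

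Two corrections are plausible. The sentence before it uses Mann-Whitney U between groups, which suggests that rank-sum was meant. The sentence after it uses McNemar, another paired test, within each group, which suggests that within-arm change was meant. Because the paragraph uses both between and within, a reader cannot safely swap one word for the other.

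The p-values for change at 3 and 6 months may therefore compare the arms or may only describe each arm alone. If they are within-arm results printed under a between-arm label, a reader may take significance in one arm and not in the other as evidence that the app works.

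**Working it through.** The plan has no power or error-rate figure for this comparison to reproduce. The check takes each possible reading in turn.

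**Inputs from the documents:** 3 against 3 CBOs (section 5.1); about 60 women (section 1.5); visits at baseline, 3 and 6 months (section 5.4); significance level 0.05 (Statistical Methods).

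**Assumptions:** 30 women per arm, 10 per CBO, no dropout; normal change scores, with effects in units of their SD; two-sided testing; intraclass correlation (ICC) of change within CBO from 0 to 0.10. The documents give no effect size and no ICC, so ranges are shown.

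**Reading 1: the test as written, with women paired across arms.** The plan gives no pairing, so an arbitrary order would have to be used. Averaged over orders, the test keeps its level (4.3% to 5.5% rejections with no arm difference), but the p-value depends on the order. Call a verdict order-dependent if between 5% and 95% of random pairings are significant. In 2,000 simulated datasets with 300 pairings each, at ICC 0, this held in 9.1% / 22.2% / 35.4% / 22.0% of datasets at a true arm difference of 0 / 0.3 / 0.5 / 0.8 SD. If the distance wording meant three matched pairs of CBOs, the smallest two-sided signed-rank p-value would be 2/2³ = 0.25.

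**Reading 2: signed-rank within each arm.** If each arm is significant with probability p, exactly one arm is significant with probability 2p(1 − p). With no true change and p = 0.05 this is 2 × 0.05 × 0.95 = 0.095, and it peaks at 0.50 when p = 0.5. Simulation with equal true change in both arms (40,000 trials per setting) gives the share with exactly one arm significant:

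| True change in both arms (SD) | 0 | 0.3 | 0.4 | 0.5 | 0.8 |
|---|---|---|---|---|---|
| ICC 0 | 0.094 | 0.446 | 0.496 | 0.390 | 0.030 |
| ICC 0.02 | 0.128 | 0.457 | 0.499 | 0.402 | 0.040 |
| ICC 0.05 | 0.182 | 0.472 | 0.497 | 0.415 | 0.061 |
| ICC 0.10 | 0.259 | 0.478 | 0.498 | 0.430 | 0.095 |

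The reverse also occurs. With true improvements of 1.2 and 0.8 SD, both arms are significant in 98.5% (ICC 0) to 95.0% (ICC 0.10) of trials, so a real difference of 0.4 SD does not show.

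**Reading 3: rank-sum, misnamed.** On individual women with no arm difference, the false-positive rate is 4.8% / 6.9% / 9.9% / 15.5% at ICC 0 / 0.02 / 0.05 / 0.10. The pairing problem is gone. What remains is the neglect of CBO randomization.

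**Candidate replacement: a t test on the six CBO mean changes, 4 df.** Its simulated false-positive rate is 5.0% to 5.1% with equal CBO sizes and 4.7% to 5.1% with sizes 6, 9, 15 against 7, 10, 13. The half-width of the 95% interval is t × √(2(1 + 9 × ICC)/30):

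- ICC 0.02: 2.776 × √(2 × 1.18/30) = 0.78 SD
- ICC 0.05: 2.776 × √(2 × 1.45/30) = 0.86 SD
- ICC 0.10: 2.776 × √(2 × 1.90/30) = 0.99 SD
- Women treated as independent: 2.002 × √(2/30) = 0.52 SD

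With distance from the PHC as a CBO-level covariate, 3 df remain (t = 3.182). The half-widths become 0.89 / 0.99 / 1.13 SD before any precision gained. A rank-sum test on 3 against 3 CBO means cannot reach 0.05: its smallest exact two-sided p-value is 2/20 = 0.10.

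**The case against.** The strongest reply is that this is probably a one-word slip in an exploratory feasibility study. Other between-arm analyses exist: the visit-by-visit tests, and a repeated-measures ANOVA aimed at the same question about change. No primary efficacy hypothesis rests on the signed-rank p-values. This stands, and it limits the severity. It does not tell a reader what the 3- and 6-month change p-values mean.

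The figures can also be called hypothetical. Nothing suggests that women were actually paired by row order, and the order-dependence shares depend on the cut-off: with 20% to 80% in place of 5% to 95% they fall to about 4% / 13% / 17% / 12%. The one-arm-significant shares count as errors only under a misreading that the plan does not prescribe. Both points are fair. The figures show what each reading would imply, not what happened. If rank-sum was meant, the test is sound apart from clustering, and clustering is a separate defect shared with the plan's other tests on individual women.

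Finally, the distance wording in section 5.1 is unclear and might mean CBOs matched in pairs. That would still pair no women. It would leave a paired CBO-level analysis with 2 df and half-widths of about 1.21 / 1.34 / 1.53 SD at ICC 0.02 / 0.05 / 0.10, before any precision gain.

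**Conclusion.** The concern holds. The named test cannot deliver the named comparison in the design described, and the documents do not show which test was run. That rests on the text alone and needs no assumption.

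The consequence depends on the reading. Within-arm tests are a legitimate description of each arm but give no between-arm result. A misnamed rank-sum test gives one, with an error rate that rises with the ICC. The simulated sizes rest on the assumed 10 women per CBO, normal change scores and no dropout. Section 10.8 foresees withdrawals, which would widen the intervals. This should be fixed; it does not by itself invalidate the trial's other comparisons.

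**What to change.** 1. State which test was run on the change scores. Keep signed-rank only for change within each arm, label it so, and draw no between-arm conclusion from it.
2. For the between-arm comparison of change at 3 and at 6 months, use an unpaired analysis that respects CBO randomization. The simplest is a t test with 4 df on the six CBO mean changes, or on baseline-adjusted CBO means, reporting the arm difference and its confidence interval. An alternative is a baseline-adjusted model with a CBO effect and about 4 df for the arm effect. The CBO effect must stay in even when its variance is estimated at zero, which happens in about 48% / 37% / 25% of simulated trials at ICC 0.02 / 0.05 / 0.10.
3. Say what accounting for distance from the PHC meant in the randomization, so that the analysis and its degrees of freedom match it.

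Renaming the test to rank-sum on individual women would cure the pairing error only.

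The cost is one sentence for the label and a short re-analysis of data already collected (six CBO means per visit). The price is wider intervals, which is what six randomized units can support.

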On repeat sign in, they will also receive questions on completion of behavioral activation homework. Women who score more than 15 will receive a prompt to view modules 1 through 4 which includes additional content on strategies for specific problems, and information on medications. They will receive information on how to seek mental health care. This ensures that women with mild to moderate depression receive initial treatment without having to overcome transportation barriers. The app will track, and graph PHQ-9 score change over time to inform need to step up care. Any woman who scores anything other than 0 on question 9 of the PHQ 9 (suicidal ideation item) will be asked to call the CHW associated with that CBO. For these women, the app will also trigger an alert to the CHW who will immediately call the patient to complete a risk assessment based on the study SI protocol. CHWs will be trained in the study safety protocol and a chain of contact will be established for each type of scenario. The woman will be escorted to the PHC if needed. Modules described above will follow the content of the Healthy Activity Program manual and will be delivered in

short (10-15 min) interactive multimedabased modules. Depending on their PHQ-9 score, women will watch 4 to 8 modules over the course of 1 to 3 months.

**Enhanced Usual Care (EUC):** For EUC, CHWs will offer standardized monthly group education (45 min) regarding the symptoms of depression, informed by training from study Investigators. All CHWs will receive education on depression symptoms and referrals.

**5.2 Recordings.** Does the research involve creating audio or video recordings?

	No	→ If no, go to question 5.3 .						

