2. Depression measured by Quick Inventory of Depressive Symptoms (QIDS SR) at baseline 3 months and 6 months. QIDS SR will be collected by a blinded / masked research assistant. Research assessments will be conducted over the phone or in the Primary Health Center to avoid unblinding of CBO randomization status (presence of tablets in the CBOs)
3. Behavioral Activation – Behavioral Activation Depression Scale (BADS). We will administer the BADS to all women to calculate adherence to behavioral activation recommendations (for intervention women) and to measure degree of behavioral activation (for Enhanced Usual Care women).
4. Mental health services utilization – At baseline, 3 months and 6 months. We will obtain information on rates of utilization of mental health services including number of contacts with mental health providers and details of medications taken.

Depression – clinical outcome (not research measure)- Patient Health Questionnaire – 9. We will obtain information on rates of utilization of mental health services including the number of contacts with mental health providers and details of medications taken.

**5.5 Data sources.** For all types of data that will be accessed or collected for this research: Identify whether the data are being obtained from the subjects (or subjects' specimens) or whether they are being obtained from some other source (and identify the source).

*If you have already provided this information in Question 5.1, you do not need to repeat the information here.*

All research measures will be obtained from subjects by research coordinators in person or by phone.

**5.6 Identifiability of data and specimens.** Answer these questions carefully and completely. This will allow HSD to accurately determine the type of review that is required and the relevant compliance requirements. Review the following definitions before answering the questions:

**Access** means to view or perceive data, but not to possess or record it. See, in contrast, the definition of "obtain".

**Identifiable** means that the identity of an individual is or may be readily (1) ascertained by the researcher or any other member of the study team from specific data variables or from a combination of data variables, or (2) associated with the information.

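### Depression categories are tested only within each arm, so the one stated category analysis cannot compare MITHRA with enhanced usual care, and its instrument and cut-off are not named

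*Combined protocol and SAP*

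**What the plan says.** The Statistical Methods section assigns each test to a target:

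- **Depression categories:** "McNemar Chi-square test was used to compare the change in the proportion of depression categories from baseline within each study group". This is the only place where the categories appear.
- **Chi-square or Fisher:** this "was used to test the association between baseline characteristics between study groups". No follow-up visit is mentioned.
- **t test or Mann-Whitney:** at each assessment, "outcome parameters were compared between study groups using independent t test or Mann Whitney U test as appropriate". The outcome parameters are listed as PHQ, QIDS, WHODAS and BADS, and are described by mean and standard deviation.
- **Wilcoxon signed rank and repeated-measures ANOVA:** change in the outcome, and outcome scores over time.

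Section 5.4 (Data variables) makes QIDS-SR the research measure: "Depression measured by Quick Inventory of Depressive Symptoms (QIDS SR) at baseline 3 months and 6 months". It labels the PHQ-9 a "clinical outcome (not research measure".

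Section 5.1 (Study procedures) gives PHQ-9 bands for routing app content. Below 5 leads to general information; then "women who score 5 – 10 will watch modules 1 and 2", "Women who score 10 – 15 will watch modules 1, 2, and 3" and "Women who score more than 15 will receive a prompt to view modules 1 through 4". The analysis does not refer to these bands. Section 5.1 also randomises three CBOs to each arm and says that distance from the primary health center is taken into account.

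**The concern.** The trial compares MITHRA with EUC. The category analysis asks a different question: did the proportions change from baseline inside each arm? Both arms have reasons to change that are not the app. Section 5.1 gives EUC women monthly group education on depression. Section 10.10 says that women above a clinical cut-off are told their result and advised to seek treatment.

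Two within-arm p-values placed side by side invite the reading that categories improved under MITHRA and not under EUC. One p-value below 0.05 and one above it does not support that reading.

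The categories are also undefined in the text available. Two depression scales are collected. Section 5.4 says that one of them is not a research measure, while Statistical Methods lists it as an outcome. The usual McNemar test needs two categories, so a split must be chosen, and the plan does not say on which scale or where.

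**Working it through.** **1. Is a between-arm category test named anywhere?** The targets listed in Statistical Methods are baseline characteristics (chi-square or Fisher), the four scales (t test or Mann-Whitney), change in the outcome (Wilcoxon), outcome scores (repeated-measures ANOVA) and depression categories (McNemar, within arm). Only the last concerns categories. Mann-Whitney could be applied to ordered categories, but the plan defines outcome parameters as the four scales.

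**2. Is a cut-off given?**

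- QIDS-SR: none in the text available.
- PHQ-9: the section 5.1 bands route app modules, and the analysis does not cite them. As printed, a score of 10 falls in two bands.
- Section 4.6 (screening positive) and section 10.10 (clinical cut-off) give no number.

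**3. Why one significant arm is not a contrast.** The documents give no category rates, so the counts here are invented. Assume 30 women per arm (60 split equally) and treat them as independent. With b women improving and c worsening, the exact McNemar p-value is twice the Binomial(b + c, ½) probability of min(b, c) or fewer.

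- One arm, b = 9, c = 1: p = 2 × (1 + 10)/1024 = 22/1024 = 0.021.
- Other arm, b = 7, c = 2: p = 2 × (1 + 9 + 36)/512 = 92/512 = 0.18.
- Improved, compared directly: 9/30 against 7/30, a difference of 30.0 − 23.3 = 6.7 points. With 16 improvers among 60, an 8–8 split has probability C(16,8) × C(44,22)/C(60,30) = 0.229. Every other split is at least as extreme as 9–7, so two-sided Fisher p = 1 − 0.229 = 0.77.

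The within-arm tests fall on opposite sides of 0.05 while the direct comparison shows nothing.

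**4. How precise would a between-arm estimate be?** Inputs: 60 women and six CBOs from the documents, hence 60/6 = 10 per CBO if enrolment is equal and complete. Assumed: proportion p above the cut-off of 0.2 to 0.5, intracluster correlation (ICC) of 0 to 0.10, and no gain from baseline adjustment. Using the true standard error:

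half-width = t × √(2p(1 − p)[1 + 9 × ICC]/30)

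With 4 degrees of freedom (df), t = 2.776:

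| ICC | p = 0.2 | p = 0.5 |
|---|---|---|
| 0 | 2.776 × 0.1033 = 28.7 points | 2.776 × 0.1291 = 35.8 points |
| 0.05 (× √1.45 = 1.204) | 34.5 | 43.2 |
| 0.10 (× √1.90 = 1.378) | 39.5 | 49.4 |

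The 4 df hold only if there is no CBO-level covariate, stratum or pairing.

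- One CBO-level baseline covariate leaves 3 df (t = 3.182): 3.182 × 0.1033 = 32.9 up to 3.182 × 0.1291 × 1.378 = 56.6 points.
- If the distance-based randomisation means three matched pairs, 2 df remain (t = 4.303): 44.4 up to 76.6 points.

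Both ranges are before any gain from adjustment or matching.

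**The case against.** The strongest reply is that depression is already compared between arms on the scores, at each visit and over time. The categories then only summarise those scores in a feasibility trial of about 60 women. The plan says openly that McNemar is within arm and nowhere says that it will be used to claim a difference from EUC. A dichotomised comparison on six CBOs would be so imprecise that it adds little.

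Much of this stands. A reader might infer that the plan has no between-arm test of depression; the score comparisons contradict that. A reader might also infer that false contrasts would occur at some calculable frequency. The documents give no rate of movement between categories, so no such frequency can be offered as the size of the problem.

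Nor can one say that no cut-off exists. The figure that accompanies the app prompts is not shown, and instruments were uploaded separately. Either could define a cut-off or settle which band holds a score of 10. The claim is limited to the text available.

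What does not stand is that a wide interval favours the present plan. The width shows what six randomised CBOs can support. Two within-arm p-values do not show it.

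**Conclusion.** The point holds for the category analysis only. As written, that analysis cannot address MITHRA against EUC, and the text available does not say which scale or cut-off defines the categories. The conflict between section 5.4 and Statistical Methods over the PHQ-9 leaves the choice of scale open.

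This is a secondary result that should be corrected; it does not undermine the trial's depression comparison. Its size rests on logic and on an invented example (0.021 and 0.18 within arms, 0.77 between), not on any rate in the documents. The between-arm replacement is imprecise: about ±29 to ±49 points on 4 df under the stated assumptions, and wider with fewer df before any gain from adjustment or matching.

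**What to change.** 1. Reconcile section 5.4 and Statistical Methods on the depression instrument. Name one analysis cut-off with its source. Statistical Methods is in the past tense, so label the cut-off post hoc if data had been seen when it was chosen.
2. Report the between-arm difference in the proportion above that cut-off at 3 and 6 months, with a confidence interval based on the six randomised CBOs. Match the degrees of freedom to the adjustment used and to what the distance-based randomisation actually was: 4 only without a CBO-level covariate, stratum or pairing. Present it as an imprecise secondary estimate.
3. Show the within-arm shifts as a descriptive table by arm, without p-values.

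The cost is SAP wording, a decision on how the randomisation enters the analysis, and one re-analysis of data already planned. No new data are needed. The downsides are the wide interval, some lost category detail and, if it applies, the post hoc label.
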